5.1.3 Recording and reporting of Adverse Events

The study-specific visit does not entail any additional risk compared to the routine visit.

Investigators will seek information on AEs during each patient contact. All events, whether reported by the patient or noted by study staff, will be recorded in the patient's medical record and in the (e)CRF within a

reasonable time after becoming aware. If available, the diagnosis should be reported on the AE page, rather than the individual signs or symptoms. If no diagnosis is available, the Investigator should record each sign and symptom as individual AEs.

The following minimum information should be recorded for each AE:

- AE description
- start and stop date of the AE
- severity
- seriousness
- causality assessment to the study interventions
- outcome

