Procedures/assessments	Phase 0: Screening and randomization		Phase 1: Lifestyle + NB with vs without VLCKD							Phase 2: Lifestyle + NB (all participants)				Follow-up (all participants)		
	Screening (In-clinic)	Randomization (in-clinic)	Remote	Remote	Remote	Remote	Remote	Remote	In-clinic (study specific)	Remote	Remote	In-clinic (Routine)	Remote	Remote	In-clinic (study specific)	In-clinic (routine)
Visit	V1	V2	V3	V4	V5	V6	V7	V8	V9	V10	V11	V12	V13	V14	V15	V16
Timing of visits (weeks)		Start	Start	W3	W4	W6	W8	W10	W10	W12	W16	W16	W20	W26	W26	W52
Visit window (days)									±30			±30			±30	±30
Lifestyle program			X		X		X			X	X		X	X		
Naltrexone/bupropion (NB)		X							X			X			X	X
VLCKD			(X) ¹	(X) ¹	(X) ¹	(X) ¹	(X) ¹	(X) ¹								
Screening assessments and randomization																
Informed consent	X ²															
Inclusion/exclusion criteria	X	X														
Randomization		X														
Anthropometric data (height, weight, waist circumference)		X							X			X			X	X

Clinical examination (Blood pressure, heart and lung auscultation, abdominal palpitation and percussion)		X							X			X				X	X
Laboratory tests																	
Fasting glucose		X							X			X				X	X
Hemoglobin A1c		X										X					X
Lipids: LDL-cholesterol, HDL-cholesterol, triglycerides		X							X			X				X	X
Liver test: AST, ALT, gamma-GT, alkaline phosphatase, total bilirubin, albumin		X										X					X
Kidney function: creatinine, eGFR		X										X					X
Thyroid function: TSH, free T4		X										X					X
Uric acid		X										X					X
Questionnaires																	
The PsyEndoAUDIT questionnaire ³		X							X			X				X	X
The PsyEndoCIDI questionnaire ³		X							X			X				X	X
The PsyEndoEDE questionnaire ³		X							X			X				X	X
The PsyEndoHADS questionnaire ³		X							X			X				X	X
Nederlandse vragenlijst voor eetgedrag ³		X							X			X				X	X
The ObesitasIPAQ questionnaire ³		X							X			X				X	X

The quality of life (SF-36) questionnaire ³		X							X				X			X	X
The outtake questionnaire															X		
Reason for discontinuation		X							X			X			X	X	
(Serious) Adverse event (S)(AE) assessment		X							X			X			X	X	

- Depending on randomization in either intervention (with VLCKD) or comparator group (without VLCKD).
- Informed Consent must be obtained prior to performing any other Trial-related procedures as part of the standard of care.
- See appendix 4 for the respective questionnaires.

I Background and Rationale

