2.1 Study objectives

[The aim of this trial is to evaluate the superiority of combined VLCKD, intensive lifestyle intervention and naltrexone/bupropion versus standard of care with naltrexone/bupropion on weight loss.]

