2.3 Secondary Endpoints

- A weight loss percentage at 10 weeks, 16 weeks and at end of trial (= 52 weeks from start)
- A proportion of patients with a weight loss percentage of 5% or more at 10, 16, 26 and 52 weeks
- A proportion of patients with a weight loss percentage of 10% or more at 10, 16, 26 and 52 weeks
- The time to reach a weight loss percentage of 5% and 10%
- The dose of naltrexone/bupropion used at 10, 16, 26 and 52 weeks and at the end of the trial
- The tolerability of VLCKD and NB
- Adherence to VLCKD and NB
- The Patient-Reported Outcome Measures (PROMs) of hunger and cravings at 0, 4, 10, 16, 26 and 52 weeks
- The change in fasting glucose, lipids and blood pressure at 10, 16, 26 and 52 weeks]

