4.8 Lifestyle

Lifestyle support, excluding the VLCKD, is offered to both the experimental and comparator arms and is regarded as part of the standard care protocol. Consequently, both groups will both have a total of 11 contact sessions, during which 30 minutes will be allocated for individual coaching and routine personal follow-up via telephone. Additionally, there are three modules comprising 12 educational presentations and 12 practical tasks designed for application in everyday life. For a comprehensive schedule outlining specific time points, please refer to Appendix 3.

5 Assessment of Safety

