5.1.3.2 Timelines for reporting

- After informed consent has been obtained and after initiation of study-related interventions:
 - All AEs and SAEs will be reported in a “written diary” in between visits during the first 12 weeks after initiation of the study-related interventions.
 - After 12 weeks until the last follow-up visit, only SAEs causally related to a study-specific intervention will be reported.

All SAEs as defined in the protocol must be reported to the Sponsor within 24 hours of the study staff becoming aware of the event. The immediate report shall be followed by detailed, written reports. The immediate and follow-up reports shall identify subjects by Study identification.

SAE details will be reported by the Investigator to the Sponsor:

- By completing the SAE form in the (e)CRF

If an authorised Investigator from the reporting site is unavailable, initial reports without causality and expectedness assessment should be submitted to the Sponsor by a healthcare professional within 24 hours

of becoming aware of the SAE, but must be followed-up by medical assessment as soon as possible thereafter.

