Appendix 2: [Pro Well VLCKD protocol]

- BMI 27+ program: 10 weeks
 - 4 weeks VLCKD strict phase: 800 kcal/day (<50g carbs, >100g proteins, vegetables with a low carb content)
 - 3 x 2 weeks of progressive increase of daily kcal: 1000 kcal, 1200 kcal (W) / 1400 kcal (M), 1500 kcal (W) / 1800 kcal (M) based on Mediterranean diet
 - Coaching minutes: 2 hours 15 minutes

Intake	30 minutes	Explanation VLCKD & App
Follow-up 1: after 3 weeks	15 minutes	Follow-up
Follow-up 2: after 4 weeks	15 minutes	Explanation 1000 kcal meal plan
Follow-up 3: after 6 weeks	15 minutes	Explanation 1200/1400 kcal meal plan
Follow-up 4: after 8 weeks	15 minutes	Explanation 1400/1800 kcal meal plan
Outtake after 10 weeks	15 minutes	Progress & Reflection

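### After week 12, SAE reporting rests on an undefined causality filter that can work differently in the two arms; and the protocol disagrees with itself on where AEs are sought

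*Protocol*

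**What the plan says.** **SAEs after week 12.** Section 5.1.3.2 has all AEs and SAEs entered in a written diary for the first 12 weeks, with no distinction by arm. From then to the last visit, "only SAEs causally related to a study-specific intervention will be reported". The paragraph that follows requires every SAE to reach the Sponsor within 24 hours and sets no causality condition. The table in 5.1.4.2 repeats the 24-hour rule but allows exceptions defined in the protocol.

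**What counts as study-specific.** The term is not defined. Section 4.8 says "Lifestyle support, excluding the VLCKD, is offered to both the experimental and comparator arms and is regarded as part of the standard care protocol". Section 2.1 describes the comparison as "versus standard of care with naltrexone/bupropion on weight loss".

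**Where AEs are sought.** Section 5.1.3 states "Investigators will seek information on AEs during each patient contact". The (S)AE row of the flowchart marks only V2, V9 (W10), V12 (W16), V15 (W26) and V16 (W52), for all participants. No remote visit is marked.

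**Use of the data.** "The tolerability of VLCKD and NB" is a secondary endpoint (section 2.3), to be analysed descriptively (section 6.2).

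**The concern.** NB is given in both arms, so its harms will be read arm against arm even if no test is planned. That reading is safe only if both arms are observed and reported by the same rule.

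Two features put this at risk. After week 12 an SAE is reported only if an investigator who knows the allocation attributes it to an intervention of an undefined kind, and one arm has an extra intervention to attribute it to. Before week 12, if AEs really are sought at every contact, the arm with more coaching calls is asked more often.

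The first matters more. An SAE that is never reported cannot be recovered by any analysis plan.

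**Working it through.** The protocol gives no SAE rate and no figure for AE capture, so there is no stated number to reproduce.

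**1. The undefined term.** Wording that points to the VLCKD as the only study-specific intervention:
- lifestyle support belongs to standard care (4.8);
- the comparator is framed as standard of care with NB (2.1);
- three visits are called routine for NB (4.5);
- the study is treated as having no IMP (7.3).

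Wording that points the other way:
- NB is the study drug (Funding and Support; section 1; 8.8) and study medication (8.8);
- elsewhere the adjective describes visits and laboratory tests that both arms have (4.5, flowchart, budget).

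The rest of section 5.1.3 generally speaks of study-related interventions. The change of adjective falls in the one sentence that filters SAEs. Section 5.1.3.3 requires SAEs suspected to be related to study-related interventions to be reported even after a patient has ended the study. On the narrow reading, the rule during weeks 12 to 52 would be stricter than the rule afterwards.

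**2. Share of follow-up under the filter.** (52 − 12)/52 = 40/52 = 76.9%.

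**3. Why the filter is not arm-neutral.** Let E be the expected non-fatal SAEs per arm in weeks 12 to 52, equal in both arms. Let b be the share attributed to NB or lifestyle, and d the share of VLCKD-arm SAEs that qualify only because the diet is a candidate cause.

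| Reading | Reported, comparator | Reported, VLCKD arm | Difference |
|---|---|---|---|
| Narrow (VLCKD only) | 0 | d × E | d × E |
| Broad (NB also counts) | b × E | (b + d) × E | d × E |

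The value of d may differ between the readings, but neither gives a neutral rule unless d = 0. On the narrow reading b × E NB- or lifestyle-related comparator SAEs also go unreported. Assuming that 5% to 15% of patients have a non-fatal SAE per year, at a constant rate and without drop-out, E = 31 × 0.05 × 40/52 = 1.2 up to 31 × 0.15 × 40/52 = 3.6 per arm. The difference then lies between 0 and E. The protocol gives no basis for d or b, and the diet ends at week 10, which may keep d small.

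**4. Contacts by week 10.** In the flowchart phase headed "Phase 1: Lifestyle + NB with vs without VLCKD":

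| | VLCKD arm | Comparator |
|---|---|---|
| Remote contacts | 6 (start, W3, W4, W6, W8, W10) | 3 (start, W4, W8) |
| Scheduled AE assessments | 2 (V2, V9) | 2 (V2, V9) |

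Appendix 2 confirms the six, including "Follow-up 1: after 3 weeks". In Appendix 3 the comparator's session after starting module 2, in month 3, may add a fourth contact near weeks 9 to 10.

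**5. Illustration of the contact imbalance.** Assume events uniform over weeks 0 to 10, each captured at the next contact with probability exp(−lag/τ), and a common W10 clinic visit. For gaps L between contacts, capture = (τ/10) × Σ(1 − exp(−L/τ)). The gaps are 3, 1, 2, 2, 2 weeks (VLCKD) and 4, 4, 2 weeks (comparator).
- τ = 2 weeks: 0.613 v 0.472, 23.0% fewer captured in the comparator.
- τ = 4 weeks: 0.772 v 0.663, 14.1% fewer.
- Diary already captures 25% of events: 14.9% and 9.8% fewer. Diary captures 50%: 8.7% and 6.1%. A perfect diary: none.

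The values of τ and the diary shares are assumptions. A fourth comparator contact would narrow the gap.

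**The case against.** **On SAEs.** A reader might infer that only the VLCKD arm has a study-specific intervention, so that no non-fatal comparator SAE can qualify after week 12. The protocol nowhere says this, and its references to NB as study drug and study medication speak against it. Nor are the 1.2 to 3.6 comparator SAEs in step 3 a difference between arms: on the same narrow reading, VLCKD-arm SAEs not attributed to the diet are dropped too. Sections 5.1.3 and 5.1.4 also have all events recorded in the eCRF, and deaths are always reported (5.1.3.5). All of this stands. It limits the size of the claim but does not make the filter neutral or define the term. Nor does the 24-hour sentence settle the conflict, because the exceptions in 5.1.4.2 leave room for the week-12 rule to override it.

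**On contacts.** The flowchart's AE assessments are the same in both arms. The extra contacts are calls by a coach, whereas 5.1.3 speaks of investigators. The diary covers the whole period of imbalance. Section 5.1.2 also takes common gastrointestinal events, headache and insomnia out of AE reporting in both arms. This is largely right: six against three counts as unequal AE questioning only if 5.1.3 prevails over the flowchart. What remains is that the two disagree, and sites could follow either.

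**Conclusion.** The point holds as a risk of unequal capture, not as a demonstrated bias. For 40 of 52 weeks, SAE reporting depends on an unblinded attribution to an undefined class of intervention, with one more candidate cause in one arm, and it contradicts the requirement beside it. On a narrow reading, NB-related comparator SAEs could go unreported. The size of any arm difference cannot be estimated from the documents.

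The AE-contact issue is secondary: an inconsistency between section 5.1.3 and the flowchart which, if resolved one way, gives six against three or four remote contacts by week 10, reduced by the diary. The percentages in step 5 show direction only.

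A reader might conclude that the tolerability comparison is biased by arm. That goes too far: the endpoint is descriptive, no between-arm test is planned, and the share of SAEs attributed to the diet is unknown.

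**What to change.** **Section 5.1.3.2.** Replace the post-week-12 sentence with one rule for both arms: every SAE from consent to the W52 visit is reported, whatever its causality. Causality is still assessed and recorded but is not a condition for reporting. Align the exceptions cell in 5.1.4.2 with this, and tabulate SAEs by arm as all-cause.

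**Section 5.1.3 and the flowchart.** Reconcile them so that systematic AE questioning takes place at the same time points in both arms: the common visits plus the diary.

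**Events learned at diet-only contacts.** Record and report them with their source flagged, and keep them in the AE table. Leaving them out would remove VLCKD-arm events, some from the strict phase in weeks 0 to 4, and could understate the diet's harms. A sensitivity table restricted to sources common to both arms can be added.

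**Cost.** Protocol wording, a few more SAE forms in a 62-patient trial, and one source field in the eCRF.

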5.1.3.1 Assessment

All AEs must be evaluated by an Investigator as to:

- **Seriousness:** whether the AE is an SAE. See above for the seriousness criteria.
- **Severity:**
 - Severity must be evaluated by an Investigator according to the following definitions:
 - *Mild* – no or transient symptoms, no interference with the subject's daily activities
 - *Moderate* – marked symptoms, moderate interference with the subject's daily activities
 - *Severe* – considerable interference with the subject's daily activities, unacceptable
- **Causality:**
 - *None* – An AE which is not related to the study-related interventions
 - *Unlikely* – An AE for which an alternative explanation is more likely (e.g. concomitant medication(s), concomitant disease(s)), and/or the relationship in time suggests that a causal relationship is unlikely
 - *Possible* – An AE which might be due to the study-related interventions. An alternative explanation is inconclusive. The relationship in time is reasonable; therefore the causal relationship cannot be ruled out.
 - *Probable* – An AE which might be due to the study-related intervention. The relationship in time is suggestive (e.g. confirmed by dechallenge). An alternative explanation is less likely.
 - *Definitely* – An AE which is known as a possible adverse reaction and cannot be reasonably explained by an alternative explanation. The relationship in time is very suggestive (e.g. it is confirmed by dechallenge and rechallenge).

5.1.3.2 Timelines for reporting

- After informed consent has been obtained and after initiation of study-related interventions:
 - All AEs and SAEs will be reported in a “written diary” in between visits during the first 12 weeks after initiation of the study-related interventions.
 - After 12 weeks until the last follow-up visit, only SAEs causally related to a study-specific intervention will be reported.

All SAEs as defined in the protocol must be reported to the Sponsor within 24 hours of the study staff becoming aware of the event. The immediate report shall be followed by detailed, written reports. The immediate and follow-up reports shall identify subjects by Study identification.

SAE details will be reported by the Investigator to the Sponsor:

- By completing the SAE form in the (e)CRF

If an authorised Investigator from the reporting site is unavailable, initial reports without causality and expectedness assessment should be submitted to the Sponsor by a healthcare professional within 24 hours

of becoming aware of the SAE, but must be followed-up by medical assessment as soon as possible thereafter.

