Pharmacotherapy is the last resort for patients before bariatric surgery. The medication used in this trial is naltrexone/bupropion (NB) with extended release. Naltrexone is an opioid antagonist that is currently used in the treatment of dependency, like alcoholism and drug addiction. Bupropion on the other hand is an antidepressant used not only in the treatment of depression but also to reduce cigarette cravings with the ultimate goal of inducing a smoking cessation. A common side effect of bupropion is weight loss. The use of both drugs separately has almost no effect on the patients' weight, but the combination of naltrexone and bupropion has showed a synergistic effect.⁽⁷⁾ NB has promising results in terms of weight loss prior to or post-bariatry with an influence on food intake, cravings and a high sense of satiety.⁽⁸⁾

Conservative therapy may already make a difference, but the majority of patients experience a lack of beneficial effect from this. For these patients, bariatric surgery (BS) may be the solution. Bariatric surgery is considered as the best treatment for morbid obesity (BMI > 40 kg/m² or BMI > 35 kg/m² with one or more weight related comorbidities) in maintaining weight loss.⁽⁹⁾ The biggest weight loss occurs the first year after surgery. Unfortunately, from then on weight stabilization or even weight regain can occur post-bariatry.⁽¹⁰⁾

Despite the fact these patients already tried conservative therapy prior to bariatric surgery, they still benefit to monitor their lifestyle in terms of physical activity, behaviour and dieting. Recent studies show a beneficial role for pharmacotherapy for post-bariatric weight regain.⁽¹¹⁾ Given the mechanism of action of NB, specific benefit can be expected in patients with insufficient reduction or relapse of food cravings and snacking after bariatric surgery. ⁽⁸⁾ Although these possible desirable effects may occur, yet patients may suffer from some side effects of the study drug. The most common adverse events are gastrointestinal disorders (nausea, vomiting, constipation), anxiety, insomnia, agitation and a headache.⁽¹²⁾

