4.4 Premature discontinuation

Participants may voluntarily discontinue from Study treatment and/or prematurely end their participation in the Study for any reason at any time. In such case the Investigator must make a reasonable effort to contact the participant (e.g. via telephone, e-mail, letter) in order to document the primary reason for this decision.

The Investigator may also decide at any time during the course of the Study, to temporarily interrupt or permanently discontinue the Study treatment if it is deemed that continuation would be detrimental to, or not in the best interest of the participant.

For participants whose status is unclear because they fail to appear for Study visits without stating an intention to discontinue or withdraw, the Investigator must make every effort to demonstrate "due diligence" by documenting in the source documents which steps have been taken to contact the participant to clarify their willingness and ability to continue their participation in the Study (e.g. dates of telephone calls, registered letters, etc.).

A participant should not be considered lost to follow-up until due diligence has been completed.

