4.7 Naltrexone/bupropion

After starting the treatment, the dose should be increased over a 4-week period as follows:

- Week 1: One tablet in the morning
- Week 2: One tablet in the morning and one tablet in the evening
- Week 3: Two tablets in the morning and one tablet in the evening
- Week 4 and onward: Two tablets in the morning and two tablets in the evening

The maximum recommended daily dose of Mysimba is two tablets twice daily with a total dose of 32 mg of naltrexone hydrochloride and 360 mg of bupropion hydrochloride. Patients with too many side effects at high dose may return to the previous dose and continue with it (maximum tolerated dose).

Naltrexone/bupropion need to be taken orally. The tablets should be swallowed whole with some water. The tablets should preferably be taken with some food. The tablets must not be cut, chewed or crushed.

The formulation of naltrexone/bupropion exists of the following:

- Tablet core: cysteine hydrochloride, microcrystalline cellulose, hydroxypropyl cellulose, magnesium stearate, lactose anhydrous, lactose monohydrate, crospovidone type A, indigo carmine aluminium paint (E132), hypromellose, disodium edetate, colloidal silicon dioxide
- Film coating: titanium dioxide (E171), macrogol (3350), talc, indigo carmine aluminium paint (E132)

The package size consists of 112 tablets naltrexone/bupropion.]

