4.7.1 Concomitant / Prohibited Medication / Treatment

Permitted:

- Concomitantly used blood glucose-lowering agents. Assess the dose to minimize the risk of hypoglycaemia because treatment with naltrexone/bupropion may result in decreased glucose levels.
- Digoxin. Monitor digoxin levels when used concurrently because bupropion may lower the plasma level of digoxin. Upon discontinuation of naltrexone/bupropion, digoxin levels may increase; monitor patient for possible digoxin toxicity.
- Concomitant administration of a serotonergic agent (SSRI or SNRI). There have been reports of serotonin syndrome, a potentially life-threatening condition. Careful observation is therefore required, especially at initiation and after each dose increase. Watch for changes in mental status,

autonomic instability, neuromuscular dysfunction, and/or gastrointestinal symptoms. If serotonin syndrome is suspected, consider discontinuing treatment.

Not permitted:

- Concomitant treatment with bupropion or naltrexone.
- Concomitant administration of MAO-inhibitors (MAOIs). There should be at least a 14-day period between discontinuation of irreversible MAOIs and initiation of treatment with naltrexone/bupropion. For reversible MAOIs, a 24-hour period is sufficient.
- Opioids such as codeine, loperamide and opioid analgesics, may be less effective. If (temporary) treatment with opioids is necessary, discontinue (or interrupt) treatment with naltrexone/bupropion. Use naltrexone/bupropion cautiously after chronic opioid use has been stopped for 7-10 days, to avoid occurrence of withdrawal symptoms.
- CYP2D6 substrates: Bupropion and hydroxybupropion are CYP2D6 inhibitors. Exposure to drugs metabolized by CYP2D6 may be increased; examples include certain antidepressants (SSRIs and many TCAs, including imipramine, paroxetine, venlafaxine), antipsychotics (haloperidol, risperidone), β -blockers (metoprolol) and class IC antiarrhythmics (flecainide, propafenone). Dose reductions of these agents may be necessary, especially with narrow therapeutic breadth (such as TCAs); consider blood level guided dosing (TDM). Exposure to citalopram increases by about 40%. Tamoxifen may be less effective due to CYP2D6 inhibition.

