5.1.2 Adverse Events that do not require reporting

In general, the following should not be reported as AEs:

- Pre-existing conditions, including those found as a result of screening (these should be reported as medical history or concomitant illness).
- Pre-planned procedures unless the condition for which the procedure was planned has worsened from the first study-related activity after the subject has signed the informed consent.

The following events are commonly observed and are therefore not considered as adverse events for the purpose of the study:

- Gastrointestinal events (constipation, nausea, vomiting, dry mouth)
- Headache
- Insomnia (especially if naltrexone/bupropion taken at night)

Although these events should not be reported to the Sponsor, these should be recorded in the patient's medical notes according to routine practice.

The following events not to be considered as SAEs are:

- Pre-planned hospitalisations unless the condition for which the hospitalisation was planned has worsened from the first study-related activity after the subject has signed the informed consent.
- Hospitalisation as part of a standard procedure for protocol therapy administration. However, hospitalisation or prolonged hospitalisation for a complication of therapy administration will be reported as an SAE.
- Hospitalisation or prolongation of hospitalisation for technical, practical, or social reasons, in absence of an AE.

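### Section 5.1.3 asks for AE enquiry at each contact, but the flowchart schedules none between Start and week 10, and section 5.1.3.2 puts even SAEs in a diary with no review time

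*Protocol*

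**What the plan says.** Three parts of the Protocol govern early AE capture.

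- **Section 5.1.3:** "Investigators will seek information on AEs during each patient contact".
- **Study flowchart:** the row "Serious) Adverse event (S)(AE) assessment" is marked at Start (V2), W10 (V9), W16 (V12), W26 (V15) and W52 (V16). It is blank at the remote contacts V3 to V8 and at V10 (W12).
- **Section 5.1.3.2:** "All AEs and SAEs will be reported in a “written diary” in between visits during the first 12 weeks". The diary is mentioned nowhere else in the Protocol, and no review time is given. After week 12 only causally related SAEs are reported. SAEs go to the Sponsor within 24 hours, counted from when study staff become aware.

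Responsibility is assigned in general terms. Section 5.1.3.1 has an Investigator evaluate every AE, and section 5.1.4 makes the Investigator responsible for recording and reporting safety events.

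Section 5.1.2 narrows what is reportable. "The following events are commonly observed and are therefore not considered as adverse events for the purpose of the study" introduces a list of gastrointestinal events, headache and insomnia. Section 1 says of NB: "The most common adverse events are gastrointestinal disorders (nausea, vomiting, constipation), anxiety, insomnia, agitation and a headache". Of those, anxiety and agitation stay reportable.

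**The concern.** The three texts do not give a site one instruction. If each patient contact includes the coach calls, the flowchart contradicts section 5.1.3. If it does not, no AE enquiry is scheduled between Start and W10, and the diary is the only planned capture in that period.

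That period holds the NB dose increases (section 4.7) and the strict diet phase (Appendix 2). For patients on an SSRI or SNRI, section 4.7.1 also says "Careful observation is therefore required, especially at initiation and after each dose increase". That last point is supporting only, because the same section lists antidepressants among drugs not permitted for lowering the seizure threshold.

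The SAE wording matters most. A participant who writes a serious event in the diary has done what 5.1.3.2 describes, but the 24-hour clock has not started because no staff member knows. The Protocol text tells participants to notify immediately only for pregnancy (5.1.3.4). Tolerability of VLCKD and NB is a secondary endpoint, and its data would depend on which text a site follows.

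**Working it through.** There is no stated figure to reproduce. The check is to set the schedule out in days.

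**Inputs.** Day 0 is Start, assuming NB and diet begin then.

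- NB steps at the start of weeks 2, 3 and 4 (section 4.7): days 7, 14 and 21.
- Strict 800 kcal phase, 4 weeks (Appendix 2): days 0 to 28.
- W10 clinic visit, window ±30 days (flowchart): 10 × 7 = 70, so day 40 to 100.
- End of the diary period (5.1.3.2): 12 × 7 = day 84.
- W16 clinic visit: 16 × 7 = day 112.
- Remote contacts after Start: W3, W4, W6, W8 and W10 in the VLCKD arm (Appendix 2). Comparator: W4 and W8 (flowchart; Appendix 3, after 1 and 2 months). W12 in both arms (flowchart).

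**Reading A: the flowchart is followed.**

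- First enquiry after Start: day 70, which is 70 − 21 = 49 days after the last NB step.
- At the earliest in-window date: 40 − 21 = 19 days after the last NB step and 40 − 28 = 12 days after the strict phase ends.
- A W10 visit on days 85 to 100 is in window but leaves no marked enquiry after Start inside the 84-day diary period.
- Diary entries from day 70 to 84 wait for W16: 112 − 84 = 28 to 112 − 70 = 42 days, on schedule.
- An unreported week-1 event (days 0 to 7) is first asked about 70 − 7 = 63 to 70 days later.

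**Reading B: remote contacts count under 5.1.3.**

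- First enquiry after Start: W3 = day 21 in the VLCKD arm, W4 = day 28 in the comparator arm.
- Enquiry times up to W12: W3, W4, W6, W8, W10, W12 = 6 in the VLCKD arm; W4, W8, W10, W12 = 4 in the comparator arm. The comparator's undated exercise session in months 3 and 4 is not counted.
- The gap is shorter, but the arms are asked unequally often, and the flowchart is wrong at every remote contact.

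**With enquiry marked at W4, W8 and W12 in both arms.**

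| | Flowchart now | With W4, W8, W12 |
|---|---|---|
| Marked enquiries after Start, to W12 | 1 per arm (W10) | 4 per arm (W4, W8, W10, W12) |
| Intervals (days) | 70 to the first | 28, 28, 14, 14 |
| Unreported week-1 event, days until asked | 63 to 70 | 28 − 7 = 21 to 28 |

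W4 still comes 28 − 21 = 7 days after the last NB step.

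**The case against.** The strongest reply is that this is a wording gap. The flowchart numbers the remote contacts as visits, so "in between visits" in 5.1.3.2 may mean between those contacts. Sections 5.1.3 and 5.1.3.2 then agree, and the flowchart row merely fails to repeat them. This stands as a possible reading, so 70 days belongs to Reading A only. It does not remove the defect, because the flowchart then needs correcting and nothing in the coaching content of section 4.6 or Appendices 2 and 3 mentions AEs.

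A reader might infer something stronger: that nobody is responsible for diary entries, or that AEs go uncollected for ten weeks. The documents do not support that. Sections 5.1.3.1 and 5.1.4 make the Investigator responsible for evaluating and recording AEs; what is unstated is when the diary is looked at. The 24-hour SAE rule applies once staff know, with a healthcare professional as backup reporter, and deaths are reported without delay (5.1.3.5). A PhD student assists with AE reporting. Patients can report sooner and have ways out: "Patients with too many side effects at high dose may return to the previous dose and continue with it", and "Participants may voluntarily discontinue from Study treatment". The consent pages are not available and may tell participants whom to call.

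It is also fair that section 4.5 describes routine NB visits as intake, W16 and W52, so the W10 visit is earlier than routine follow-up. Tolerability is analysed descriptively only (section 6.2), and that the two sites would in fact diverge is a possibility, not something the Protocol shows.

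**Conclusion.** The point holds as a mismatch between text and schedule, together with an SAE route that should not run through a diary. Followed as drawn, the flowchart puts the first scheduled enquiry after Start at day 70 (day 40 to 100), after all NB dose steps and the strict diet phase. On the broader reading of 5.1.3 the gap is 21 days (VLCKD) or 28 days (comparator).

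The delays assume that NB and diet begin at Start, that visits other than W10 are on schedule, and that neither the patient nor a hospital reports earlier. They are therefore upper limits for visits held on schedule. The consequence is for patient safety and for the completeness of the tolerability data. The primary endpoint, weight loss at 26 weeks, is unaffected. This is worth correcting because it is cheap, not because safety oversight is absent.

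**What to change.** 1. **Section 5.1.3.2:** limit the diary to non-serious AEs, and state that participants are told to contact the site immediately about any serious event, as 5.1.3.4 does for pregnancy. For SSRI or SNRI users, name the warning signs in 4.7.1.
2. **Flowchart and section 5.1.3:** mark AE enquiry and diary review at W4, W8 and W12 in both arms, as well as at the clinic visits. Set the last remote review by day 84. Appendix 3 times that contact at 3 months, about day 91, which would fall after the diary period ends.
3. **Who does it:** site study staff, with evaluation by the Investigator. The PhD student is one option, but for AZ Sint-Jan Brugge the Protocol gives the student pseudonymised data only, so local staff would probably be needed there. Coaches should not be the ones to elicit AEs, since their programme is supplied by the company whose diet is being tested.
4. **Coaches:** forward any event they hear of to the site, at once if possibly serious.
5. **eCRF:** record whether an event came from a scheduled enquiry or was volunteered. The VLCKD arm has extra coach calls at W3, W6 and W10, and this lets tolerability be compared on equal terms.

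The cost is a protocol amendment with possible EC review (section 8.7), a short instruction to coaches, and a few minutes of existing staff time per contact. No clinic visit is added. Events during titration before W4 would still rely on the notification instruction in item 1.
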